3.3 ASSESSMENT OF EFFICACY

- Specification of the efficacy parameters: please see § 1.1 and 3.1.
- Methods and timing for assessing, recording, and analyzing efficacy parameters: Please see § 1.2, 3.1, 8.1, 8.2 and 8.3.

The efficacy endpoints included in this clinical study were selected to optimize the characterization of the effects of rhNGF in moderate to severe DED in order to obtain robust evidence of the clinical efficacy of the treatment and its relevance for the patients. For this reason, subjective and objective measures are collected after 4 weeks of treatment and at the end of the Follow-Up period (week 8, V5). This study is looking at the effects of rhNGF on multiple markers of DED because it is expected to see efficacy in measures of tear production, in measures of CCI and CCI general DED symptoms and visual acuity. The prediction of efficacy, the study design and the associated SAP are based on previous clinical data obtained by the Sponsor that have enabled the preparation of this trial and the proposed assessments. In particular, the primary endpoint definition at week 8 (V5) (after 4 weeks of treatment and 4 weeks Follow-Up period) is based on clinical observations made during the studies NGF0118 and NGF0121 that showed an effect on the symptoms after the end of the treatment period. A combination of secondary and exploratory efficacy endpoints is making

sure the effect of the treatment is well characterized at week 4 (V4; 28±1 days from Baseline visit) and at week 8 (V5; 56±2 days from the Baseline visit - end of 4 weeks of Follow-Up).

4 TRIAL DESIGN

4.1 DESCRIPTION OF TRIAL DESIGN

This trial is a 4-weeks Phase II, multi-centre, randomized, double-masked, vehicle-controlled, parallel-group, dose-finding clinical trial with 4 Weeks of Follow-Up to evaluate safety and efficacy of a new formulation of recombinant human Nerve Growth Factor (rhNGF) eye drop solution at two different concentrations in patients with dry eye disease (DED). It is designed as a superiority clinical trial to assess the efficacy and safety of a new ophthalmic formulation rhNGF as compared to a vehicle in patients with dry eye disease (DED). This is a prospective Phase II trial for a new formulation of two concentrations (C mcg/mL and C mcg/mL) of rhNGF eye drops. The new formulation is specifically prepared to allow the administration of CCI concentrations of rhNGF eye drop solution to CCI rhNGF induced CCI experience in patients with DED. The new formulation can be stored at CCI °C further improving the conditions of storage and manipulation of the drug.

- The study is carried out in multiple centers (USA and Italy).
- Male or female patients aged ≥18 years of any race/ethnicity and eye color will be screened for enrollment to minimize bias in population sampling. All patients successfully enrolled will be randomized by Interactive Response Technology (IRT); both the investigator and the patient will be masked to the treatment arm assigned. Patients will be randomized 1:1:1 to either of the two concentrations of rhNGF formulation (C mcg/mL or C mcg/mL) or vehicle. The total number of patients to be enrolled in the study will be about 291, 97 per group to target 276 evaluable patients (92 per group). The total number has been obtained considering a 5% rate of patients not evaluable for primary analysis after enrolment. Considering a screen failure rate of 20%, approximately 350 subjects need to be screened in order to have 291 patients enrolled and at least 276 patients evaluable.
- The study is divided in 4 phases: Screening & Start of Run-In period (day -12±2, Visit 1); Run-in Period (day -12±2/Screening Visit 1 to day 1/Baseline Visit 2); Treatment Period (day 1/Baseline Visit 2 to week 4/day 28 ± 1, Visit 4); Follow-up Period (End of Treatment visit 4 at week 4 to End of Follow-up - End of Study visit 5 at week 8, day 56 ± 2). Procedures for inclusion will be performed at both Visit1 (Screening) and Visit 2 (Baseline).
- At Screening visit (Visit 1, day -12±2), eligible patients will be instructed to discontinue all topical ophthalmic medications and during the Run-In period they will only be allowed to use the Study Product (vehicle) ophthalmic solution provided by the Sponsor. This solution needs to be prepared daily and administered by the patient in both eyes as eye drops solution TID (at approximately 6-hours intervals).
- At Visit 2 (baseline visit) a Study Eye will be determined. Namely, the Study Eye is the worst eye: assuming that all the inclusion/exclusion criteria are met in both eyes, the worse eye (Study Eye) will be determined at the Baseline visit based on the lower Schirmer I (without anesthesia) score. If the Schirmer I score of both eyes is identical, the Study Eye will be determined based on the worse NEI staining score for cornea and conjunctiva (first NEI score for cornea then for conjunctiva). If both eyes are identical,

then simply the right eye will be considered the Study Eye.

- The treatment period will start at Baseline visit (Visit 2, day 1) and the IMP will be administered as an eye drops solution to be prepared daily and administered by the patient TID at approximately 6-h intervals in both eyes for a treatment period of 4 weeks. During the 4 weeks of masked treatment only the administration of IMP is allowed. The use (number of drops/day) of IMP will be clearly documented in a Patient Diary and in the eCRF. Different administration frequencies will be recorded and considered as protocol deviation. The treatment period will be completed at Visit 4 (day 28 ± 1) and it will be followed by a 4 weeks Follow-Up period.
- During this Follow-Up period patients will be requested to administer preservative free artificial tears (AT) (NIMP) provided by the Sponsor TID at 6-h interval in both eyes for a 4-week period until Visit 5 (day 56 ± 2 , week 8). During the 4 weeks of Follow-Up period only the administration of AT provided by the Sponsor is allowed. The use of AT will be clearly documented in a Patient Diary and in the eCRF. Different administration frequencies will be recorded and considered as protocol deviation. Any topical ophthalmic concomitant treatment initiated during the Study period (between Visit 1 and Visit 5) must be documented on the concomitant medication log and represents a protocol deviation. The End of Study Trial visit (EOS) is expected at Week 8. The maximum total study duration will be about 10 weeks.
- Patients will be evaluated at Screening visit (day -12 ± 2 , V1) after which they will enter a Run-In period with the Study Product vehicle (from day -12 ± 2 to day 1). Evaluations will continue at Baseline visit (day 1, V2), week 2 (day 13 ± 1 , V3), week 4 (day 28 ± 1 , EOT (V4)), and at week 8 (day 56 ± 2 follow-up and EOS (V5)). At the investigator's discretion, any patient could be seen for an Unscheduled Visit for safety evaluation. An Early Exit Visit could be done in case of premature study discontinuation. In case of treatment discontinuation, patients will be asked to complete the assessments at the planned visits as per Protocol. In case of premature discontinuation of the study, the subject will be required to participate at the Early Exit Visit that will have the same assessments of Visit 4 (in case of early treatment and study discontinuation before Visit 4) or the same assessments of Visit 5 (in case the discontinuation from the study will occur after the ending of the treatment but before the expected Visit 5). A flag will be inserted in the eCRF to define if the Visit 4 or 5 is a per protocol visit or if it is done as Early Exit Visit.
- The trial design follows the principles of Quality by Design (QbD) with respect to eligibility criteria, randomization, masking, data quantity, endpoints, data integrity, IMP handling and administration, site feasibility, safety reporting, data monitoring and delegation of responsibilities. Detailed evaluations and timing are presented in § 1.2, 1.3 and 8.

4.2 RATIONALE FOR TRIAL DESIGN

The study has been designed as a dose-finding, superiority clinical trial with a Run-In period using vehicle since this is a new formulation of rhNGF. During the Run-In period of 12 ± 2 days, patients will only use the new vehicle formulation (three times a day) in both eyes to provide the minimum amount of lubrication needed in DED patients while ensuring appropriate wash-out from any other previous topical treatment effect. This trial tests two CC concentrations of a new CCI rhNGF formulation (C mcg/mL or C mcg/mL) in patients with DED. This new formulation allows the

administration of [CC] doses of rhNGF in eye drops. This new formulation simplifies the conditions of drug manipulation and drug storage. The storage of the new formulation of ophthalmic solution containing the active principle rhNGF is now at [CCI] °C. This is reducing patient burden with respect to storage and handling of IMP in this study and provides an important advantage for the accessibility to the drug.

The rationale for testing [CCI] concentrations of rhNGF stems from previous clinical trials where a [CCI] concentration of rhNGF was used ([C] mcg/mL) and up to 48% of patients reported eye pain and 21% eyelid pain (NGF0121 - PROTEGO-1). Therefore, a new formulation of rhNGF was prepared that allowed [CCI] concentration with the goal of consequently [CCI] TEAEs for patients. Hence, this trial aims to determine the safety and efficacy of 2 [CCI] concentrations of rhNGF in dry eye patients.

Furthermore, a shorter duration of treatment was selected (4 weeks) with TID dosing instead of an 8-week long treatment with dosing six times a day (NGF0216).

The trial design is based on clinical observations made during previous clinical studies. Namely NGF0118, a 4-week, Phase II, multicenter, randomized, double-masked, vehicle-controlled, parallel group study with 12 weeks of follow-up to evaluate safety and efficacy of recombinant human Nerve Growth Factor (rhNGF) eye drops solution versus vehicle in patients with moderate to severe dry eye (DED) that was completed in 2021. In this study there were significant improvements in the rhNGF TID group when compared to vehicle on Schirmer test II and on assessments of TFBUT. In addition, rhNGF 4 weeks treatment had clinically relevant delayed beneficial effects compared with vehicle on SANDE scores (and other scores) which showed significant improvement during the follow-up period but not during the treatment period. This clinical observation is in line with the proposed mechanism of action for rhNGF on DED and DED symptoms and requires a specific demonstration during this clinical study with a primary endpoint on SANDE Global score after 4 weeks of Follow-Up period. SANDE score repeated measures will be collected 4 weeks apart: at Baseline, after 4 weeks of treatment and after 4 weeks of Follow-Up.

NGF0118 also demonstrated that TID dosing had better durability of sustained improvement in symptoms and signs in DED as compared to BID dosing prompting the definition of a TID regimen of administration at approximately 6h-intervals during this study.

In addition to testing the two concentrations of rhNGF ([C] mcg/mL and [C] mcg/mL), this study incorporates a vehicle control group. The vehicle control group has been incorporated in this study in order to demonstrate efficacy of our new formulation in improving symptoms and signs in patients with dry eye, a disease where it is known that a relevant placebo effect may be expected and the presence of an inactive control group favors the correct interpretation of any treatment effect.

5 TRIAL POPULATION

Male and female patients with diagnosis of dry eye who fulfill the inclusion/exclusion criteria will be enrolled in the study.

5.1 INCLUSION CRITERIA

- 1) Male or female aged ≥ 18 years of any race/ethnicity and eye color.
- 2) A diagnosis of dry eye disease at least 6 months before enrollment (current use or recommended use of artificial tears for the treatment of dry eye).
- 3) Moderate-to-severe dry eye characterized by the following clinical features:

- a) Symptoms Assessment in Dry Eye (SANDE) questionnaire global score ≥ 50 , and
 - b) Schirmer-I test without anesthesia > 2 mm and < 10 mm/5 minutes, and
 - c) Total corneal fluorescein staining grade ≥ 3 (NEI scale) and/or total conjunctival lissamine green staining score ≥ 3 assessed by the National Eye Institute (NEI) grading system, and
 - d) Fluorescein Tear Film Break-Up Time (fTBUT) < 10 seconds. The same eye must have fulfilled all the above criteria.
- 4) Best corrected distance visual acuity (BCDVA) score on ETDRS chart of ≥ 0.1 decimal units (≤ 1.0 logMAR) in each eye at the time of study enrollment
 - 5) Negative pregnancy test in females of childbearing potential.
 - 6) Only patients who satisfy all informed consent requirements will be included in the study; the patient and/or his/her legal representative must have read, signed, and dated the informed consent document before any study-related procedures are performed; the informed consent form signed by patients and/or legal representatives must have been approved by the IRB for the current study.
 - 7) Have the ability and willingness to comply with study procedures.

5.2 EXCLUSION CRITERIA

- 1) Inability to speak and understand the local language sufficiently to understand the nature of the study, to provide written informed consent, and to allow the completion of all study assessments.
- 2) Evidence of an active ocular infection in either eye.
- 3) Presence of any other ocular disorder or condition requiring topical medication during the entire duration of the study.
- 4) Possibility of the need for ocular surgery at the time of inclusion in the study or anticipated ocular surgery expected during the participation in the study.
- 5) History of severe systemic allergy or severe ocular allergy (including seasonal conjunctivitis, AKC, VKC) or chronic conjunctivitis and/or keratitis other than dry eye.
- 6) Ocular scarring due to irradiation, alkali burns, Stevens-Johnson syndrome and ocular cicatricial pemphigoid.
- 7) Destruction of conjunctival goblet cells such as in Vitamin A deficiency.
- 8) Severe blepharitis or obvious inflammation of the lid margin.
- 9) Intraocular inflammation defined as Tyndall score > 0 .
- 10) Medical history of tumor malignancy in the previous 3 years
- 11) Systemic disease not stabilized within 1 month before the Screening visit (e.g., diabetes with glycemia out of range, thyroid malfunction) or judged by the investigator to be incompatible with the study (e.g., current systemic infections) or with a condition incompatible with the frequent assessment required by the study.
- 12) History of a serious adverse reaction or significant hypersensitivity to any drug or chemically related compounds or had a clinically significant allergy to drugs, foods, CCI [REDACTED] eyedrop or other local anesthetics or other materials, including ocular vital dyes, tropicamide eye drops, commercial artificial tears.
- 13) Known or suspected allergy to CCI [REDACTED] and/or any other component of the new rhNGF formulation.
- 14) Fertile patients (i.e., not surgically sterilized, or postmenopausal women for at least 1 year) are excluded from participation in the study if they do not practice abstinence from heterosexual intercourse as per usual and customary lifestyle, or are unwilling to use an acceptable form of contraception such as condom with spermicidal cream or jelly for males, or for females if they meet any one of the following conditions:
 - a) Currently pregnant (positive urine pregnancy test at screening or baseline visits) or planning to become pregnant during the duration of the treatment phase of the clinical

- trial.
- b) Patient is breastfeeding.
 - c) Unwilling to use birth control measures such as mechanical barrier methods (spermicide in conjunction with a barrier such as a condom or diaphragm or intrauterine device) during the entire course of and 30 days after the study treatment periods, or,
 - d) Unwilling to continue to use highly effective birth control measures such as hormonal contraceptives (oral, implanted, transdermal, or injected) during the entire course of and 30 days after the study treatment periods.
- 15) Any concurrent medical condition that, in the judgment of the principal investigator, might interfere with the conduct of the study, confound the interpretation of the study results, or endanger the patient's well-being.
 - 16) Contact lenses or punctum plug use in either eye during the washout, treatment and follow-up phases of the study (previous use is not an exclusion criteria but must be removed and discontinued at the Screening visit)
 - 17) Medical history of drug addiction or alcohol abuse (>1 drink /day for women and >2 drinks /day for men following USDA dietary Guidelines 2020-2025).
 - 18) Any prior ocular surgery including but not limited to amniotic membrane transplant, refractive (PTK/LASIK/Epi-LASIK/LASEK/SMILE), palpebral, cataract surgery, trabeculectomy, vitrectomy and pan-retinal photocoagulation (PRP) within 90 days before the Screening visit.
 - 19) Participation in a clinical trial with a new active substance, including medical devices, during the previous 60 days.
 - 20) Participation in another clinical trial study at the same time as the present study.

5.3 SELECTION OF STUDY EYE

At Visit 2 (Baseline visit) a Study Eye will be determined. Namely, the Study Eye is the worst eye: assuming that all the inclusion/exclusion criteria are met in both eyes, the worse eye (Study Eye) will be determined at the baseline visit based on the lower Schirmer I (without anesthesia) score. If the Schirmer I score of both eyes is identical, the Study Eye will be determined based on the worse NEI staining score for cornea and conjunctiva (first NEI score for cornea then NEI score for conjunctiva). If both eyes are identical, then simply the right eye will be considered the Study Eye.

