3.6. Definition of Study Eye

The Study Eye is the worst eye: assuming that all the inclusion/exclusion criteria are met in both eyes, the worst eye (Study Eye) will be determined at the baseline visit based on the lower Schirmer I (without anesthesia) score. If the Schirmer I score of both eyes is identical, the Study Eye will be determined based on the CCI. If both eyes are identical even considering NEI, then simply the right eye will be considered as the Study Eye.

4. General Statistical Considerations

Tabulations of summary statistics, graphical presentations, and statistical analyses will be performed with SAS® software, version 9.4 or higher.

Descriptive statistics for continuous variables in summary tables will include the number of patients in the analysis (n), mean, standard deviation (SD), median, first quartile (Q1), third quartile (Q3) and range (minimum, maximum). Descriptive statistics for qualitative variables in summary tables will include counts and percentages per category. If appropriate, 95% confidence intervals (CIs) around the mean or the proportion will be presented. The number of patients with missing data will be presented under the “Missing” category. Missing values will not be included in the denominator count when computing percentages. When continuous data are summarized, only the non-missing values will be evaluated for computing summary statistics. Any exception will be declared.

In general, regardless the strategy of the analysis described in [Section 8](#), a summary table with descriptive statistics will be produced for each efficacy endpoint. Summaries will be generated for observed cases, on absolute values and changes from baseline at each timepoint for continuous variables, on proportions at each timepoint for qualitative variables.

For the purpose of efficacy analyses in this trial, the statistical analysis (both descriptive and inferential) will be done on the Study Eye which is determined at baseline visit (visit 2). Details will be provided in the statistical analysis outputs as notes. In case the analysis involves both eyes, it will be clearly declared. This consideration only applies to the assessments that are done at individual eye level and does not apply to any assessment done at patient level (e.g., SANDE, CCI ...).

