6.3. Dry Eye History

Dry eye history will be summarized by eye (study eye and fellow eye) for time from diagnosis (years), cause of dry eye, receiving of prior treatment, and eye affected by moderate to severe dry eye. Time from diagnosis will be calculated by date of informed consent – date of diagnosis for each eye + 1, then divided by 365.25. Partial dates are treated according to below rules:

- if month and day are missing, set to 01-July of that year;
- if only day is missing, set to 15th of that month.

Dry eye history will be presented in a by-patient listing by site as collected per eCRF.

7. Treatments, Medications, and Procedures

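### One qualifying eye is enough for entry, but the Study Eye rule presumes that both eyes qualify and never restricts the choice to a qualifying eye

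*Protocol*

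**What the plan says.** **Eligibility (Protocol 5.1, repeated in the synopsis).** Criterion 3 has one patient-level part, a SANDE Global Score of at least 50, and three eye-level parts:

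- 3b: "Schirmer-I test without anesthesia > 2 mm and < 10 mm/5 minutes"
- 3c: "Total corneal fluorescein staining grade ≥ 3 (NEI scale) and/or total conjunctival lissamine green staining score ≥ 3"
- 3d: "Fluorescein Tear Film Break-Up Time (fTBUT) < 10 seconds"

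It closes with "The same eye must have fulfilled all the above criteria". Criterion 4, on visual acuity, is worded differently: it must hold "in each eye at the time of study enrollment".

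**Study Eye (Protocol 5.3, also the synopsis and 4.1).** The text reads "the Study Eye is the worst eye: assuming that all the inclusion/exclusion criteria are met in both eyes". The eye with the lower Schirmer-I at Visit 2 is chosen. Ties go to the worse corneal staining, then the worse conjunctival staining, then the right eye. SAP 3.6 keeps the same premise: "assuming that all the inclusion/exclusion criteria are met in both eyes, the worst eye (Study Eye) will be determined at the baseline visit".

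**Use of the Study Eye.** Protocol 10.6.1 and SAP sections 4 and 8 run the eye-level efficacy analyses on the Study Eye. SAP section 4 exempts patient-level assessments such as SANDE. Compliance is also computed for the Study Eye (Protocol 6.5, SAP 7.3.1), and gross non-compliance removes a patient from the Per Protocol set.

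**The concern.** The two rules do not fit together. Eligibility needs one eye that meets 3b to 3d; the Study Eye rule starts from two. No section says what to do when only one eye qualifies, and none says that the Study Eye must be a qualifying eye.

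The lower bound in 3b makes this more than loose wording. An eye can fail for being too dry, and the selection rule prefers the drier eye. The eye on which the patient qualified can therefore be passed over for one outside the defined population.

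At stake are the three key secondary endpoints (Schirmer-I responder, Schirmer-I change and corneal staining change, all at Week 4), which carry the trial's aim of showing an effect on signs. The other eye-level secondary endpoints and Study Eye compliance, hence Per Protocol membership, are exposed too.

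**Working it through.** **The plan's own figure.** The plan gives no figure on this point. Its sample size can be checked, and stands apart from it. The SANDE difference is 28.2 − 17.4 = 10.8, and the pooled SD is √((26.36² + 20.29²)/2) = 23.52. At one-sided alpha 0.0125 the normal approximation needs 91 per group, and a Welch t-test with 92 per group has 80.2% power. Then 92/0.95 = 96.8, so 97 per group, and 276/0.95 = 290.5, so 291. SANDE has no eye, so the choice of eye does not enter.

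**The logic.** Let the qualifying eye have Schirmer-I S, so 2 < S < 10, and let the non-qualifying fellow eye have Schirmer-I F.

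- F ≤ 2: then F < S always, and the rule takes the fellow eye.
- F ≥ 10: then F > S always, and the rule takes the qualifying eye.
- 2 < F < 10: the fellow eye fails on staining or tear break-up time. The rule takes it if F < S, or if F = S and the tie-breaks favour it.

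**Worked cases.** The values are illustrative. Each eye is given as Schirmer-I (mm) / corneal staining / conjunctival staining / fTBUT (s). The right eye qualifies in every case.

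| Case | Right eye | Left eye | Left fails on | Rule picks |
|---|---|---|---|---|
| A | 6/5/4/5 | 2/5/4/5 | Schirmer-I floor | Left |
| B | 7/5/4/5 | 5/2/2/5 | Staining | Left |
| C | 7/5/4/5 | 5/5/4/11 | fTBUT | Left |
| D | 6/5/4/5 | 12/5/4/5 | Schirmer-I ceiling | Right |
| E | 6/4/4/5 | 6/5/4/12 | fTBUT (Schirmer-I tied) | Left |

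**Frequency.** The documents give no between-eye data, so any percentage is an assumption. One simulated scenario takes median Schirmer-I 6 mm, mean staining 4 (SD 3) and median fTBUT 5 s. The literal rule then picks a non-qualifying eye in 19.1%, 17.0% and 13.4% of eligible patients at between-eye correlations of 0.5, 0.7 and 0.85. With other assumed distributions and correlations of 0.5 to 0.95 the result runs from about 0.2% to about 26%. On 291 patients that is 0.002 × 291 = 0.6 to 0.26 × 291 = 76. A range this wide says only that the share must be counted.

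**The case against.** The best defence is that the opening clause is a condition: rank by Schirmer-I when both eyes qualify, and otherwise the rule does not apply. That reading is fair. A reader might infer from cases A to C that the plan certainly analyses the wrong eye; the text does not support that much. On the conditional reading the one-eye patient is undefined, not misassigned. But 10 to 15 sites then have no written instruction and may settle the case differently, so the gap remains on either reading.

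The defence can also say that the consequences are bounded, and this stands. The Study Eye is fixed from Visit 2 findings before assigned treatment begins, so selection works alike in all arms and does not inflate type I error. Confirmatory testing of the key secondaries happens only after the primary succeeds. The Schirmer-I models adjust for baseline Schirmer-I.

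Finally, SAP 6.3 plans a by-eye summary of "eye affected by moderate to severe dry eye". This shows that disease status is recorded for each eye. It is weak evidence that one-eye qualifiers were expected, and the point does not need it.

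**Conclusion.** The conflict holds on the text alone. Taken literally, the rule places a non-qualifying eye in the eye-level analyses when the fellow eye has Schirmer-I of 2 mm or less, or when it fails staining or fTBUT and ranks as worse on Schirmer-I or the tie-breaks. Taken conditionally, there is no rule for the one-eye patient. A fellow eye with Schirmer-I of 10 mm or more is never chosen. The primary endpoint, the sample size and type I error are unaffected. The number of patients concerned is unknown, and no loss of power can be computed.

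Two further inferences are tempting and should not be drawn:

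- **That an eye at 2 mm or less faces a special hurdle of 8 mm to count as a responder.** SAP 8.2.1.1 codes the Week 4 response as a change from baseline of at least 10 mm, and the SAP governs where the documents differ (SAP section 1). Under that coding every eye needs the same gain.
- **That the rule is what fills the corneal staining endpoint with eyes that have no room to improve.** Criterion 3c is and/or, so an eye that qualifies on conjunctival staining may have no corneal staining. Restricting the Study Eye to qualifying eyes would not remove such eyes.

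**What to change.** In the synopsis, Protocol 4.1 and 5.3, and SAP 3.6, state that the Study Eye must itself meet criteria 3b to 3d. If only one eye qualifies, that eye is the Study Eye. If both qualify, the present Schirmer-I ranking and tie-breaks apply. If both eyes were always meant to qualify, say so in the synopsis and Protocol 5.1 instead.

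Before unmasking:

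1. Count from masked Visit 2 data how many patients have one qualifying eye and how many flags the rule would change.
2. Re-derive the flag from the eye-level data already collected.
3. Confirm that fellow-eye Week 4 and Week 8 data exist for those patients. The Visit 1 and 2 examination lists specify each eye and the Visit 4 and 5 lists do not, although SAP section 8 plans listings of fellow-eye assessments.
4. Report the number of changes and keep the original flag as a sensitivity analysis.

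The cost is one rule in the documents and a masked re-derivation, with no new patients or procedures. The downside is that some flags change, and with them Study Eye compliance, possibly Per Protocol membership, and the tables split by study and fellow eye (for example ocular adverse events and ophthalmic medications).
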